 American Indian or Alaska Native  
 Native Hawaiian and Pacific Islander 8)

What is your height?

9) What is your weight (in pounds)?

10) Do you have **asthma**? Y/N

11) Do you have **cancer**? Y/N

12) Do you have **chronic obstructive pulmonary disease (COPD)**? Y/N

13) Do you have **diabetes**? Y/N

14) Do you have a **heart condition**? Y/N

15) Do you have **high blood pressure**? Y/N

16) Do you have **kidney disease** or **reduced kidney function**? Y/N

17) Have you ever had an **organ transplant**? Y/N

18) Do you have **sickle cell disease**? Y/N

19) Are you a **smoker**? Y/N

20) Do you take **beta blockers**? Beta blockers are medicines designed to reduce heart rate, which can affect vital sign readings. For example: Tenormin, Cardiacor, Emcor, Betaloc, Inderal, or Angilol.  
 Y/N

21) Please enter any feedback about this survey:

Thank you for filling out your welcome survey! Your responses have been recorded.

Daily Survey:

Each day Current Health will ask you a **brief series of questions** about symptoms and decisions that may be related to COVID-19. Your daily response and information collected from the wearable device will create the most accurate picture of your health. This survey should take **less than 5 minutes** to complete.

1) In the **past 24 hours**, did you have (or continue to have) any of the following symptoms:

- ✦ loss of smell or taste
- ✦ dry cough
- ✦ sore throat
- ✦ fever or feeling feverish
- ✦ chills
- ✦ muscle aches
- ✦ diarrhea
- ✦ nausea
- ✦ other, please specify (free text)

[FOR EACH YES] Is your <symptom> better or worse than yesterday?

- ✦ Categorical scale: Much worse, Worse, The same, Better, Much better

- 2) Due to how you are feeling **today**, do you plan to speak to a health care provider?
- 3) Due to how you are feeling **today**, do you plan to go to the hospital?
- 4) Do you feel as though you have completely recovered from COVID-19 as of today?

Thank you for completing your daily survey! Your responses have been recorded.

For our study participants, data will be collected “blind”. The participant will not be able to see their data in real time, and no data will be reviewed or acted upon by the study team unless there is a clinically indicated trigger elicited by the system. These triggers exist to prompt the capture of study-specific information, not to direct patient care.

1. Reduction in SpO2 below 88% for 60 minutes

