## 6.6. Timing of Outcome Assessments

The frequency and timing of all the relevant study assessments is considered from the time the participant CH kit arrives to 30 days of observation or a met outcome.

Study Task	Timeline
Kit Setup	Day 1
Participant Intake Survey	Day 1 to Day 3
*Daily Survey	Daily
CRA Adherence Checks	Day 1 to Day 30 ongoing
Vital signs captured by CH wearable	Day 1 to Day 30 ongoing
Outcome Verification	Day 1 to Day 30 ongoing and 30 days after observation period ends

\*Daily symptom questionnaire will close if not completed within a given number of hours. Participant will still be able to fill out the following day's daily symptom questionnaire.

Variables collected from study assessments will be generally as follows:

- Demographic – Categorical
- Medical history and medication – Boolean
- Symptom presence – Boolean (“Much better” to “Much worse”)
- Symptom severity – Ordinal categorical

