### 7.3. Adherence and Protocol Deviations

A study participant will be considered fully adherent to study protocol if they:

- Wear the CH device for at least 20 hours a day, at least 6 days a week;
- Answer the questions on the tablet at least 6 days a week;
- Return wearable kit and device.

Adherence metrics will be presented in absolute and percentage terms. Both measures will account for how long a participant is in the study. For example, a participant that is observed the entire 30 days will have a possible total of 720 hours (30 days x 24 hours) and 30 answered tablet symptom surveys. This participant's minimum adherence level would be 600 hours of device wear and at least 26 completed symptom surveys. A participant that meets an outcome much earlier due to hospitalization after 7 days would still be considered adherent if prior to hospitalization they wore the device 140 hours and completed 6 symptom surveys.

A summary table will generally be presented with the following variables per participant:

Participant ID
Time in trial (hours)
Hours of CH device observation
Wearable adherence percentage
Time in trial (days)
Number of surveys completed
Survey adherence percentage
Overall study adherence (Y/N)

Following collection all participants this information will be aggregated to the CONSORT flow chart metrics.

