Smoker	smoker	Binary: Yes, No
Intake survey feedback	intake_survey_feedbackk	Long free text
†Daily Survey		
Loss of smell or taste	loss_smell_taste	Binary: Yes, No
Is your loss of smell or taste better or worse than yesterday?	loss_smell_taste_likert	Categorical: Much worse, Worse, The same, Better, Much better
Dry cough	dry_cough	Binary: Yes, No
Is your dry cough better or worse than yesterday?	dry_cough_likert	Categorical: Much worse, Worse, The same, Better, Much better
Sore throat	sore_throat	Binary: Yes, No
Is your sore throat better or worse than yesterday?	sore_throat_likert	Categorical: Much worse, Worse, The same, Better, Much better
Fever or feeling feverish	fever	Binary: Yes, No
Is your fever better or worse than yesterday?	fever_likert	Categorical: Much worse, Worse, The same, Better, Much better
Chills	chills	Binary: Yes, No

Are your chills better or worse than yesterday?	chills_likert	Categorical: Much worse, Worse, The same, Better, Much better
Muscle aches	muscle_aches	Binary: Yes, No
Are your muscle aches better or worse than yesterday?	muscle_aches_likert	Categorical: Much worse, Worse, The same, Better, Much better
Diarrhea	diarrhea	Binary: Yes, No
Is your diarrhea better or worse than yesterday?	diarrhea_likert	Categorical: Much worse, Worse, The same, Better, Much better
Nausea	nausea	Binary: Yes, No
Is your nausea better or worse than yesterday?	nausea_likert	Categorical: Much worse, Worse, The same, Better, Much better
Are there any other symptoms or differences in health you would like to report?	daily_survey_feedback	Long free text
Will you speak to a healthcare provider due to worsening symptoms today?	self_reported_provider_care	Categorical: Yes, No, Maybe
Will you go to the hospital due to worsening symptoms today?	self_reported_hospital	Categorical: Yes, No, Maybe
Do you feel as though you have completely recovered from COVID-19 as of today?	self_reported_recovery	Categorical: Yes, No, Maybe

\*Participant Intake Survey questions are to be completed by participant one time.

†Daily Survey questions are asked once a day at the same time each day.

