To assess the algorithm performance, algorithm testing on a total of 1,000 participants will be conducted. This cohort of 1,000 testing participants will be held entirely separate from the training participants to avoid any possible data snooping or data mining bias in the study. In machine learning it is typical to obtain initial testing cohort results to determine if the model created from the training data is performing well. After the first 100 participants in the testing cohort are monitored for 30 days, the algorithm will be tested for understanding initial performance. As more participants are recruited into the study, follow up algorithm testing will occur for each 100 participants that are added to the testing cohort. To avoid any potential issues with multiple testing, only the most recent testing metrics (AUC/ROC, PPV, Brier Scores, etc.) will be reported. Therefore, the unique full test set will only be run *once*.

Although the outcome of the participants in the validation set is known, the outcomes will be initially ignored, as if researchers did not know participant outcome. This simulates what researchers know about a participant preceding the participant's outcome. The testing participants' collected variables (demographic, medical history, continuous data from wearable, and symptom data) will be run through the developed algorithm. The algorithm will return probabilities of the study outcomes. The algorithm's probabilities will then be compared with the true outcome of the participant recorded by the CRA.

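### In the available SAP, Stage 2 testing fixes no prediction time, lead time or horizon, so the AUC may rest on data running up to admission and does not test early prediction

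*Combined protocol and SAP*

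**What the plan says.** - **Inputs at test.** In SAP 9.2, Stage 2, the test participants' "collected variables (demographic, medical history, continuous data from wearable, and symptom data) will be run through the developed algorithm". The returned probabilities are then compared with the outcome on record. Protocol Stage 2 says the same.
- **Timing.** The only statement about time is "This simulates what researchers know about a participant preceding the participant's outcome". No day, lead time, look-back window or horizon follows.
- **One prediction per person.** SAP 5.2 ties each individual Brier score to one participant.
- **Length of record.** SAP 6.6 has assessments run "from the time the participant CH kit arrives to 30 days of observation or a met outcome". SAP 7.3 gives an example: "A participant that meets an outcome much earlier due to hospitalization after 7 days would still be considered adherent". SAP 7.3.2 sends adherent participants to both training and testing.
- **Recovery.** SAP 5.1 makes recovery a primary outcome, defined by days elapsed since symptom onset or the positive test and by symptom-free days.
- **Intention items.** The daily survey asks "Will you go to the hospital due to worsening symptoms today" (SAP 8.5). The protocol's wording is "do you plan to go to the hospital" (Study Design).
- **Gate.** SAP 5.2 and 6.4 finalise and deploy the model if AUC is significantly above 0.75 with reasonable specificity, sensitivity and calibration.

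**The concern.** The stated purpose is to identify people likely to become severely ill while they are still in the community. That requires a prediction made at a known time, from data recorded before it, about a later period. As written, a participant's input can be the whole record up to the outcome. For an admitted participant this includes the last hours before admission.

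The last value, the maximum and the number of symptom days then all depend on when the record stopped, and the outcome itself is one reason for stopping. A model can score well on such features and give no usable warning. Training and test cohorts are built the same way, so holding the second cohort out does not expose the problem. At stake is the meaning of the AUC that decides deployment.

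**Working it through.** **1. The plan's own figures.** 1,000 × 0.10 = 100 events and 900 non-events per cohort (SAP 6.3). The adherence examples in SAP 7.3 also reproduce: 7 × 20 = 140 hours and 7 × 6/7 = 6 surveys for the participant hospitalised after 7 days; 30 × 20 = 600 hours and 30 × 6/7 = 25.7, so 26 surveys, for the full 30 days. Both count as adherent and both enter the model, with 600/140 = 4.3 times as much minimum wear time in one as in the other. No figure in the documents measures the effect of this.

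**2. What the gate requires.** Hanley–McNeil: SE = √{[A(1−A) + (m−1)(a−A²) + (n−1)(b−A²)]/(mn)}, with a = A/(2−A) and b = 2A²/(1+A). For A = 0.80, m = 100, n = 900: SE = √[(0.16 + 2.64 + 63.93)/90,000] = 0.0272, and the 95% lower limit is 0.80 − 1.96 × 0.0272 = 0.747. The lower limit passes 0.75 at an observed AUC of about 0.8035 (0.7955 one-sided; the SAP does not state sidedness).

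**3. Record span as the only information.** Exit days are assumed uniform; the documents give no distribution. AUC = P(admission day < exit day) + ½P(equal).

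| Admission days | Non-event exit days | AUC |
|---|---|---|
| 1–14 | 14–30 | 1 − 0.5/238 = 0.998 |
| 1–14 | 7–30 | 304/336 = 0.905 |
| 1–30 | 14–30 | 365.5/510 = 0.717 |
| 1–20 | 5–20 | 192/320 = 0.600 |
| 1–14 | 1–14 | 0.500 |
| 1–30 | 7–21 | 202.5/450 = 0.450 |

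The effect ranges from none to almost perfect separation, depending on exit times that the plan does not predict.

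**4. The same-day intention item, if it were used.** Let s and f be the shares of admitted and other participants who ever answer yes (both assumed). AUC = 0.5 + (s − f)/2 and SE = 0.5√[s(1−s)/100 + f(1−f)/900].
- s = 0.60, f = 0.02: AUC 0.79, SE 0.0246, lower limit 0.742. Fails.
- s = 0.62, f = 0.02: AUC 0.80, SE 0.0244, lower limit 0.752. Passes.
- s = 0.40, f = 0.05: AUC 0.675. Fails.
- s = 0.70, f = 0.05: AUC 0.825, lower limit 0.780. Passes.

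**5. Recovery.** This step needs no assumed rates. The outcome is partly defined by symptom-free days, and daily symptom data are a named input. Without a cut-off, the inputs can contain part of the outcome definition. The AUC hypothesis in SAP 5.2 concerns hospitalisation, so this affects the reported recovery performance and not that gate.

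**The case against.** **The SAP says that inputs precede the outcome.** It does, and that bars data recorded after the outcome. It still permits data from the hour before, so the point stands.

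**A time rule may exist elsewhere.** SAP section 12 says temporal-data text was added and cites a section 9.5, while the contents list and the available text stop at 9.2. This is a real limit: the claim can only be that no rule appears in the available SAP. The rolling average or median in SAP 5.2 smooths the signal over an unspecified number of periods; it does not set a prediction time.

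**Record span is not a listed variable.** True of protocol Table 2 and SAP 8.5 to 8.7. However, span also enters through maxima, last values and counts, which no text restricts.

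**Recovery can end records early.** Also true. The 14 days run from symptom onset or the positive test, not from kit arrival, and the protocol accepts a negative PCR with no minimum time. Non-event records may therefore stop well before record day 14, which is why step 3 includes values near 0.5.

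**A reader might infer that the hospital-intention item goes through the model.** No text says so. The Stage 2 sentence lists symptom data, the protocol's survey introduction separates symptoms from decisions, and Table 2 lists only symptoms. On the other side, SAP 6.6 calls the survey a symptom questionnaire ("Daily symptom questionnaire will close if not completed within a given number of hours"), the protocol screens variables by significance, and nothing excludes the item. Its use is possible but not stated. An answer given before admission is also a very late predictor, not the outcome itself.

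**A reader might also infer that leakage alone would carry the model through the gate.** The documents do not support that. The gate needs about 0.80 observed, not 0.75, plus the other criteria, and steps 3 and 4 contain failures as well as passes.

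**Conclusion.** The point holds in limited form. In the available SAP, the Stage 2 evaluation has no prediction time, lead time or horizon, and the length of each record depends on the outcome. The resulting AUC can be inflated and does not answer the early-prediction question, even if the 0.75 gate is met.

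The size cannot be fixed from the documents. Under assumed exit days, span alone gives about 0.60 to 0.998 where admissions tend to precede other exits, and about 0.5 or below where they do not. The intention item, if used, would pass the gate alone only from about s = 0.62 at f = 0.02. These figures rest on 100 events and 900 non-events; analysing only adherent participants would leave fewer and raise the observed AUC needed. The conclusion is conditional on no time rule existing in SAP text outside the available copy.

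**What to change.** First confirm whether the temporal-data text and section 9.5 named in the change log contain a time rule. If they do, restore it to the SAP. If not, add to SAP 9.2 before Stage 2 is analysed:

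1. One primary prediction time: either a landmark counted from device activation, or a time-updated prediction with a stated minimum lead time. Set the horizon to day 30.
2. Only data time-stamped before that time, with features computed over a look-back window of equal length for everyone.
3. An at-risk set of participants who are event-free and at home at that time.
4. AUC, PPV and Brier score reported at that time, with the AUC >0.75 gate applied there.
5. `self_reported_hospital`, `self_reported_provider_care` and `self_reported_recovery` left out of the primary model, or a model containing them reported separately.

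The cost is SAP wording and programming. The reported AUC will probably be lower, and with a landmark the early events drop out. At an observed AUC of 0.80 with 900 non-events, the 95% lower limit is 0.747 with 100 events, 0.741 with 80 and 0.725 with 50 (the number lost is an assumption). A time-updated prediction with a minimum lead time would keep more of the early events but is harder to program and report.

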## 10. Summary of Study Data

All continuous variables will be summarized using the following descriptive statistics: n (non missing sample size), mean, standard deviation, median, maximum and minimum. The frequency and percentages (based on the non-missing sample size) of observed levels will be reported for all categorical measures.

Major reporting aspects of the study will be the CONSORT diagram to understand participant recruiting funnel, baseline participant characteristics tables, the Bayesian network model and its performance features, and participant predict risk scores and probabilities as outputs from the model.

## 11. Reporting Conventions

Describe reporting conventions, for example the precision used for reporting p-values and other numeric values. Example:

P-values  $\geq 0.001$  will be reported to 3 decimal places; p-values less than 0.001 will be reported as "<0.001". The mean, standard deviation, and any other statistics other than quantiles, will be reported to one decimal place greater than the original data. Quantiles, such as median, or minimum and maximum will use the same number of decimal places as the original data. Estimated parameters, not on the same scale as raw observations (i.e. regression coefficients) will be reported to 3 significant figures.

## 12. Summary of Changes to the SAP

In version 2, the hypothesis was more explicitly stated with specific target metrics that need to be met for model standards and deployment. Additional information regarding structural and parameter learning were added for further context. Information about incorporation of temporal data was added. In Version 3 information about how to randomize the for data modeling if study recruitment is not met is considered in section (9.5)

